Primary objective:

The primary objective of this trial is to evaluate the effectiveness of LAMP-based enhanced malaria detection in improving pregnancy outcomes as measured by birth weight, neonatal anemia, maternal anemia, and stillbirth.

Secondary objective:

The secondary objectives are:

- a. To determine the proportion of asymptomatic MiP cases revealed by microscopy, RDT and LAMP
- b. To evaluate the impact of the intervention in terms of malaria-associated placental damage as evaluated by placenta weight and placental malaria.
- c. To evaluate the performances of IllucidX LAMP(ultrasensitive) compared to the approved method using the samples from the trial.
- d. To compare the diagnostic performance of microscopy, RDT and LAMP against qRT-PCR in MiP.
- e. To decipher parasitic genotypes that may impair diagnostic test performances and treatment efficacy using parasite whole-genome sequencing.

Section 3: Trial Methods

1. Trial design

The study is a prospective diagnostic study of malaria in pregnant women. The goal is to determine whether: (i) LAMP provides a clinically measurable benefit compared to current first-line diagnostic test of Giemsastained microscopy and whether (ii) enhanced case detection of asymptomatic mothers with LAMP has added value in terms of outcomes. We hypothesize that addition of LAMP to one arm will be of greater benefit than microscopy alone due to additional LAMP sensitivity. We further hypothesize that enhanced case detection by screening asymptomatic mothers at each antenatal visit will be of additional value in treating malaria. Both symptomatic and asymptomatic first and second trimester mothers will be included in the study and individually randomized to one of two arms: standard of care or enhanced cased detection arms using LAMP for malaria. Mothers will be enrolled during a twelve-months period from March 2021 to July 2022 then followed until 28 days after delivery

2. Randomization

Women will be screened for eligibility and randomized either in the Standard of Care (SOC, 1/3 of included women) arm or in the intervention arm (2/3 of included women).

Randomization will be implemented at each health center. Stratification per parity (primiparus, second pregnancy and \geq 3 pregnancy) will be implemented to avoid confounding factor of acquired immunity for MiP variants.

3. Sample size

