The sample size calculation for this study is based on detecting a difference in the proportion of deliveries with a low birth weight (LBW), which was felt to be the most clinically important outcome variable. The prevalence of deliveries with a LBW in Ethiopia was estimated to be 17.3%. An alpha of 0.05 was selected with an allocation ratio of 3:1 in favor of the enhanced case detection arm. The study will be powered to detect an absolute difference in the proportion of deliveries with a LBW of 5%, so a proportion in the enhanced case detection arm of 12.3% compared to 17.3% in the standard of care arm. Using a continuity correction and an attrition rate of 20%, a total sample size of 2583 is required to achieve 80% power.

4. Framework

The LAMPREG trial aims to show the superiority of the intervention arm.

5. Statistical Interim analyses and stopping guidance

a. Two formal interim analysis are planned

- One formal statistical interim analysis is planned when 25% of the total inclusion target number (n = 646) is reached. This interim analysis will focus on the inclusion baseline data and the follow-up data available to date.
- Another formal statistical interim analysis is planed when 25% of the inclusion target reached the end of the protocol (28 days post-natal delivery). This analysis will be partial since post hoc gold standard molecular testing will not be available yet.
 - b. Adjustments planned of the significance level due to interim analysis

The prevalence of malaria in the study sites is paramount for the study outcome. Interim analysis will tailor this factor and decision of site closure or site initiation may be taken.

c. Details of guidelines for stopping the trial early

The LAMPREG trial interim results will be presented to an advisory board. LAMPREG is not a new interventional drug trial, and therefore unlikely to be subject to study termination. The Ethiopian NRERC ethical board waived the need of independent data monitoring and safety committee for LAMPREG.

6. Timing of final analysis

The final analysis of clinical data in the SOC *vs.* LAMP arm will be performed after the last follow up is completed, in a time frame of 6 months (secund semester of 2022), given that data entry is performed according to the protocol.

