The laboratory testing post trial (gold standard testing, parasitic variant assessment) is scheduled for 2 years post sample collection, with analysis and publication of results within a 3-year frame (end of 2022- first semester of 2023).

7. Timing of outcome assessments

The scheduled of ANC visit is given in the study protocol (v1.5 – see table 5).

Section 4: Statistical Principles

1. Confidence intervals and p-values

All applicable statistical tests will be two-sided and will be performed using a 5% significance level.

All confidence intervals presented will be 95% and two-sided.

2. Adherence and Protocol Deviations

Protocol adherence is defined by the completion of all ANC visit as per study arm (included treatment course completion for women eligible) and the follow-up of the newborn for 28 days post-delivery.

Nonadherence is defined by the number of missed visits, the loss to follow-up or the absence of recorded birth weight.

Protocol deviation is defined as:

- Non-administration of malaria treatment for LAMP positive women in the intervention arm
- Incomplete treatment administration for any treated women
- Loss to follow up or partial course of ANC visit

3. Analysis population

The intention-to-treat population will include all randomized patients, according to the study arm they were randomized in.

Section 5: Trial population

1. Screening data

The following summaries will be presented for all screened patients: inclusion time frame, number of the screened expecting mothers, number of mothers recruited per month, the reason for non-recruitment. This summary will be presented overall and by study center.

2. Eligibility

Eligibility criteria are presented in the study protocol v1.5.

To summarize, all pregnant women >18 years old, with gestational age < 27 weeks and attending ANC care in any of the study centers is eligible to the study

3. Recruitment

The "CONSORT" diagram comprising the number of people screened, eligible, consented, randomized, receiving their allocated intervention (malaria diagnostic and treatment) and followed to delivery will be presented with the study results.

4. Withdrawal/Follow-up - level of withdrawal

The level of consent withdrawal will be tabulated (classified as "consent to continue follow-up, sample and data collection" "consent to continue follow up and data collection", "complete –no further follow-up or

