Secondary outcomes were signs of placental malaria infection at delivery, defined as a composite of maternal malaria (detection of infection in peripheral blood with post hoc gold standard testing) or placental malaria (detection of infection in placental blood with microscopy, molecular testing for active infection, or malaria pigment in blood smear monocytes for signs of past infection)

Secondary outcomes include maternal anemia (any: hemoglobin level <11 g/dL; moderate: hemoglobin level <9 g/dL) during each ANC visit and at delivery. We will use the categories "no anemia", "mild anemia", "moderate anemia" and "severe anemia" using the reference values for each pregnancy trimester. Values will be disaggregated according to gestational age.

Secondary outcomes during pregnancy comprised maternal malaria, detected with any method and by each method separately. This outcome was further stratified by patent infection (positive microscopy or malaria rapid diagnostic test) and sub-patent infection (negative microscopy and malaria rapid diagnostic test and positive LAMP–PCR). Morbidity outcomes assessed during pregnancy comprised clinical malaria (documented or history of fever plus positive malaria rapid diagnostic test or microscopy) and unscheduled clinic visits for any reason and for all reasons unrelated to malaria.

2. Analysis methods

Mean values of quantitative variables will be compared using a two-sided t-test with a significance of p < 0.05. We will use a negative binomial model to assess the effect of asymptomatic malaria screening using the number of (i) both microscopic and submicroscopic and (ii) submicroscopic *P. falciparum* infections occurring during pregnancy with an adjustment for the confounding variables. Multiple test correction will be implemented.

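### SAP 6.2 compares means by arm with an unadjusted t-test although randomisation is stratified by parity and run at each health centre: valid, but some precision is given up

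*SAP*

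**What the plan says.** SAP Section 6.2 (Analysis methods) states for continuous outcomes: "Mean values of quantitative variables will be compared using a two-sided t-test with a significance of p < 0.05". Section 4.1 adds: "All applicable statistical tests will be two-sided and will be performed using a 5% significance level". No covariate, stratum or repeated-measures term is named. Section 6.2 also promises a correction for multiple tests, without saying which.

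SAP Section 6.1 lists mean birth weight, mean gestational age and mean birth-weight-for-gestational-age Z score among its primary study outcomes. It defines maternal haemoglobin through anaemia thresholds and categories, assessed "during each ANC visit and at delivery". Protocol Section 5.2 lists absolute birth weight, maternal haemoglobin and neonatal haemoglobin as secondary outcomes.

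On the design, SAP Section 3.2 says: "Randomization will be implemented at each health center". It then stratifies by parity in three levels.

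Adjusted models do appear in SAP Section 6.2: log-binomial regression by malaria status, quantile regression for the effect of malaria infection on birth weight and gestational age, and a negative binomial model for numbers of infections. Protocol Section 5.8 plans risk ratios by arm for the primary outcome.

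**The concern.** When randomisation is balanced within strata that predict the outcome, the between-stratum part of the variation no longer contributes to the difference between arms. A two-sample t-test still counts it. Its standard error is then too large, its confidence interval too wide and its true type I error below 5%. If balance within strata is only loose, the unadjusted estimate itself is noisier than it need be. Either way, terms known at randomisation are left out of the comparison they were meant to protect.

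At stake is some precision on mean birth weight and the other continuous newborn outcomes. For mean maternal haemoglobin there is also a specification gap: up to four values per woman are scheduled, and no text says how they combine into one comparison of arms.

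**Working it through.** **1. The plan's own figure.** SAP Section 3.3 and Protocol Section 5.6 assume "a proportion in the enhanced case detection arm of 12.3% compared to 17.3% in the standard of care arm", with an "allocation ratio of 3:1 in favor of the enhanced case detection arm", and conclude: "Using a continuity correction and an attrition rate of 20%, a total sample size of 2583 is required to achieve 80% power". With k = 3, p1 = 0.173, p2 = 0.123, pooled p = (0.173 + 3 × 0.123)/4 = 0.1355:

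- n (standard of care) = [1.960 √((4/3) × 0.1355 × 0.8645) + 0.842 √(0.1431 + 0.1079/3)]² / 0.05² ≈ 511.4.
- With continuity correction: (511.4/4) × [1 + √(1 + 8/(3 × 511.4 × 0.05))]² ≈ 538.
- Total 4 × 538 = 2152, and 2152 × 1.2 = 2582.4, rounded up to 2583.

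The figure reproduces. It concerns low birth weight only. Neither document gives a sample size, standard deviation or power for mean birth weight or haemoglobin.

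**2. Which stated method estimates the effect of arm on a mean?**

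| Method | Exposure or outcome as stated | Adjusted arm effect on a mean? |
|---|---|---|
| t-test (SAP 6.2) | quantitative variables | no, unadjusted |
| log-binomial (SAP 6.2) | malaria status as exposure | no |
| quantile regression (SAP 6.2) | malaria infection as exposure | no |
| negative binomial (SAP 6.2) | number of infections | no |
| risk ratio (Protocol 5.8) | arm, primary outcome | no, a proportion |

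So the t-test is the only stated comparison of means by arm.

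**3. Birth weight.** Inputs: pilot means 3059 g and 2965 g, n = 150 and 50, p = 0.1478 (Protocol Section 3, Table 4). With 198 degrees of freedom, t = 1.453, so SD = 94 / (1.453 × √(1/150 + 1/50)) ≈ 396 g. This comes from one pilot site, so it excludes between-site variation.

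Evaluable women: 2583 × 0.8 = 2066, or 516.6 and 1549.8 at 3:1. Unadjusted SE = 396 × √(1/516.6 + 1/1549.8) = 20.1 g. Detectable difference at 80% power = (1.960 + 0.842) × 20.1 ≈ 56 g.

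After adjustment, SE is multiplied by √(1 − R²), where R² (assumed) is the share of variance explained by parity and centre:

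| R² | SE (g) | SE reduction | Detectable difference (g) |
|---|---|---|---|
| 0.02 | 19.9 | 1% | 55.8 |
| 0.05 | 19.6 | 3% | 55.0 |
| 0.10 | 19.1 | 5% | 53.5 |
| 0.20 | 18.0 | 11% | 50.4 |

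SAP Section 3.2 allocates one third to standard of care and two thirds to intervention, which conflicts with 3:1. At 2:1 the unadjusted detectable difference is 51.8 g; the proportional gains are the same.

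In the limit of perfect balance within strata, the true type I error of the nominal 5% t-test is 2 × [1 − Φ(1.960/√(1 − R²))]: 4.8% at R² = 0.02 and 2.8% at 0.20.

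**4. Maternal haemoglobin, if its mean is compared by arm.** Assume a common correlation r between visits. Variance relative to a single-visit t-test:

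- One visit, adjusted for a baseline value: 1 − r². At r = 0.5 this is 0.75, a variance cut of 25% and an SE cut of about 13% (√0.75 = 0.866). For r = 0.4 to 0.6 the variance cut is 16–36%.
- Mean of four visits, no baseline: (1 + 3r)/4. At r = 0.5 this is 0.625, an SE cut of about 21% (√0.625 = 0.791). For r = 0.4 to 0.6 the factor is 0.55 to 0.70, an SE cut of 26% to 16%.

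The four visits are 26, 32 and 36–38 weeks and delivery (Protocol Section 5.2, Table 5). The second comparison sets an average over pregnancy against a value at one visit, so part of its gain is a change of estimand.

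**The case against.** The strongest reply is that nothing here is wrong in the sense of biased. An unadjusted t-test after stratified randomisation is valid and, if anything, conservative. That stands.

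A reader might go further and infer that the trial will run a separate t-test on haemoglobin at every visit, discarding a baseline value it already holds. The documents do not support that:

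- The t-test sentence names neither birth weight nor haemoglobin. Mean birth weight is a listed SAP outcome, so the test plainly reaches it. For maternal haemoglobin the SAP specifies anaemia categories; a comparison of means comes only from the protocol's outcome list. The pilot's Table 4 did test each visit separately, but that is not the plan for this trial.
- Table 5 lists no haemoglobin at visit 1, and the baseline variables in SAP Section 5.6 omit it. An entry value is implied by the exclusion below 8 g/dL (Protocol Section 5.4), but it may not be kept as study data. The SAP also cites protocol version 1.5, whereas the protocol at hand is version 1.1.
- Combining baseline adjustment with averaging at r = 0.5 gives variance factors of 0.417 (three visits) and 0.375 (four), an SE 35–39% smaller. That figure needs a baseline value that may not exist, rests on an assumed correlation, and mixes in the change of estimand.

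Two further cautions stand. Visits 1 and 2 may be combined for women presenting in the second trimester; their 26-week value is then a baseline and cannot also be a follow-up. For women enrolled shortly before 26 weeks, the intervention has had little time to act on that value, so a plain average over visits may dilute the effect. Finally, SAP Section 3.2 uses the word stratification only for parity. Randomising at each centre makes centre a design factor in practice, but the documents do not describe the lists or blocks.

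**Conclusion.** The point holds as one of efficiency and specification. The only stated comparison of means by arm omits the randomisation factors, and the adjusted models elsewhere in SAP Section 6.2 do not fill the gap because arm is not their exposure.

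For birth weight the loss is probably modest: an SE about 1–11% larger than needed for an assumed R² of 0.02–0.20. For mean maternal haemoglobin the possible gain is larger, but it depends on an assumed correlation, on whether mean haemoglobin is compared at all, and on whether a pre-randomisation value is recorded. A reader should not infer bias, an invalid test, or any effect on the low-birth-weight comparison or the 2583.

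**What to change.** In SAP Section 6.2, replace the t-test sentence for comparisons by arm:

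- **Mean birth weight, birth-weight Z score, gestational age and neonatal haemoglobin:** linear regression on arm, parity stratum and health centre, with robust standard errors. Report the adjusted difference with its 95% confidence interval; keep the t-test as descriptive only.
- **Mean maternal haemoglobin, if compared by arm:** one linear mixed model over the scheduled post-randomisation visits, with arm, visit, arm-by-visit, parity stratum and health centre. Name in advance the single contrast to be tested. Add pre-randomisation haemoglobin only if it is recorded, and treat a value taken at a combined visit 1 and 2 as baseline. The anaemia categories in SAP Section 6.1 still need their own analysis.
- State in SAP Section 3.2 whether centre is a stratification factor, and reconcile the allocation ratio with Section 3.3.

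The cost is a few sentences in the SAP and a few lines of Stata or R, with no extra participants or procedures. A mixed model also uses women with some visits missing, which helps because SAP Section 6.3 does not impute outcomes. Whether enrolment haemoglobin is captured should be checked first; if it is not, the model stands without it.

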5.7.4. Loop-mediated isothermal amplification (LAMP)
5.8. Statistical Analysis Plan20
5.9. Data analysis and interpretation
5.10. Benefits and beneficiaries of the proposed study22
5.11. Dissemination of findings
5.12. Ethical Considerations
6.0. WORK PLAN
7.0 English Version of Questionnaire2
8.0 References

SUMMARY

Background: Malaria is one of the major public health problems in sub-Saharan Africa. It contributes significantly to maternal and fetal morbidity and mortality in affected countries.

Objective: The aim of this study is to evaluate the impact of enhanced case detection using molecular testing (LAMP) on maternal and infant morbidity and mortality in a prospective study design.

Method: A pragmatic randomized control diagnostic trial will be conducted from October 2020 until October 2021 in pregnant mothers at sites in Ethiopia. Both symptomatic and asymptomatic first and early second trimester pregnant women will be included in the study and individually randomized to either standard of care or enhanced cased detection arms using LAMP for malaria. Women (n=2583) will be enrolled during a twelve-months period encompassing the peak transmission seasons and then followed until delivery. In the standard of care arm, venous blood sample will be collected from each study participant and the presence of *Plasmodium* infection will be diagnosed by microscopy in symptomatic patients. Pregnant women who test positive for malaria will be referred and treated for malaria with quinine or artemisinin combination therapies (ACTs) as per national guidelines. In the intervention arm, mothers who are symptomatic or asymptomatic will be tested by a commercially available CE-approved LAMP malaria test and microscopy/RDT for malaria at each clinic visit and treated if positive by any test. Pregnant mothers who require treatment will be referred and treated with either quinine or artemisinin combination therapy (ACTs) as per national guidelines. The primary outcome is the proportion of deliveries with low birth weight based on WHO definition, with secondary outcomes of:(i)absolute birth weight; (ii) maternal hemoglobin;(ii) neonatal hemoglobin at birth;(iv) neonatal mortality; (v) stillbirth; and (vi) prematurity in each arm of the study.

Result Dissemination plan: The results of this study will be presented at national and international scientific conferences. It will also be published in a reputable journal.

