symptomatic and asymptomatic first and second trimester mothers will be included in the study and individually randomized to one of two arms: standard of care or enhanced cased detection arms using LAMP for malaria. Mothers will be enrolled during a twelve-months period from October 2020 to October 2021 and then followed until 28 days after delivery. Given the rate of pregnant mothers at the locations, we anticipate that the required minimum of 2583 mothers will be enrolled in the study during the study period. In the first standard of care arm, venous blood sample will be collected from each study participant and the presence of *Plasmodium* infection will be diagnosed by microscopy in symptomatic patients. Pregnant women who test positive for malaria will be referred and treated for malaria with quinine or ACTs as per national guidelines. In the second (test) arm, mothers whether symptomatic or asymptomatic will be tested by a commercially available CE-approved LAMP malaria test (Meridien Biosciences, Illumigene Malaria M kit, Cincinatti, USA) and Human Diagnostics LoopAMP (Wiesbaden, Germany) at each clinic visit in addition to RDT/microscopy. The commercial LAMP tests can distinguish P. falciparum and P. vivax and treatment will be given according to national guidelines. The purpose of doing all tests in the intervention arm is to determine how many additional cases LAMP identified. The primary outcome is the proportion of deliveries with low birth weight, with secondary outcomes of: (i) absolute birth weight; (ii) maternal hemoglobin; (ii) neonatal hemoglobin at birth (Standard Hgb testing from peripheral blood or finger prick); (iv) neonatal mortality; (v) stillbirth; and (vi) prematurity in each of the two arms. Additionally, signs of current or past *Plasmodium* sequestration in the placenta will be evaluated.

[figure not shown]

Figure 1: Flowchart summarizing randomized trial

There will be a total of at least five antenatal visits (mandatory). Emergencies (medical consultation outside the planned visit) will be recorded for each included woman. Visit 1 and 2 may be combined for mothers who present in the second trimester. The following table summarizes the procedures to be conducted at each visit.

Visit #	Time frame	Aim	Action for the study
1	Visit at health care center	Inclusion	Enrolment and randomisation
2	26 weeks gestation	Follow up	Malaria testing as per inclusion arm (2mL venous blood on EDTA) +ANC regular care Maternal Hgb

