5.7.2. Blood sample collection and processing

For microscopy, two milliliters of venous blood will be collected from each study participant using EDTA anticoagulant test tube. Soon after venous blood collection, a drop of blood will be taken for RDT test and another two separate drops of blood will be placed on frosted microscope slides to prepare thin and thick blood films. For LAMP, two milliliters of venous blood will be collected from each study participant using EDTA anticoagulant test tube. LAMP will be performed at the respective health centers based on the manufacturer's recommendation (Meridian Diagnostics, and Human Diagnostics). Dried blood spot (DBS) samples will also be collected from all individuals by using two drops of blood placed on a Whatmann filter paper. DBS will be stored in AHRI for further testing if required. DBS will also be sent to the University of Calgary, Canada (cf MTA) for ultrasensitive malaria technique (qRT PCR) and parasitic whole genome sequencing. For placental infection assessment, placental blood will be collected on anticoagulant after delivery.

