For any adverse event, women will be given the contact of the local study coordinator. Community Health Worker will be sensitive to the study. At the following ANC visit, women will be encouraged to report any side effect or concern to the study staff. Each local study site coordinator will summarize any adverse event on a monthly basis and transmit the corresponding information to the national coordinator. Proper pharmacovigilance notification will be operated to the health authorities if necessary.

The LAMPREG clinical trial aims to evaluate the impact of active detection of both sub microscopic symptomatic MiP and asymptomatic (microscopic and submicroscopic) MiP. In this trial, even asymptomatic and submicroscopic MiP will be treated for *Plasmodium* spp infection as if they were uncomplicated MiP cases. The proposed used drugs fall under the drugs approved by Ethiopia Food, Medicine and Health Care Administration and Control Authority and have been proven safe during pregnancy. Importantly, the benefits of the treatment overpass the risk due to treatment induction. Information sheet and informed consent were modified to provide information regarding the treatment risk. Importantly, drugs prescription will be at the discretion of the physician assessing the women, and women safety will be the main priority of the medical staff in charge of the study.

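### The infection count meant to measure the effect of screening has no counting rule and no named test, and the direction of its result depends on both

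*SAP*

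**What the plan says.** SAP Section 6.2 (Analysis methods): "We will use a negative binomial model to assess the effect of asymptomatic malaria screening using the number of" P. falciparum "infections occurring during pregnancy with an adjustment for the confounding variables". Two versions are planned: microscopic plus submicroscopic infections, and submicroscopic infections alone. The section gives no rule for telling a continuing infection from a new one, no rule for positives after treatment, no test, and no term for visits tested or time at risk. It can also be read with the count as an exposure, not as the outcome.

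SAP Section 6.1 does not settle the test: "Secondary outcomes during pregnancy comprised maternal malaria, detected with any method and by each method separately".

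The arms differ in what ends an infection. In the control arm (Protocol 5.2), "infection will be diagnosed by microscopy in symptomatic patients". In the intervention arm, "mothers whether symptomatic or asymptomatic will be tested by a commercially available CE-approved LAMP malaria test" at each clinic visit, and women are tested "and treated if positive by any test" (Protocol Summary, Method). Protocol 5.12 adds that "even asymptomatic and submicroscopic MiP will be treated for" as uncomplicated cases would be.

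A common test is within reach. Under Protocol 5.7.2, dried blood spot (DBS) "samples will also be collected from all individuals by using two drops of blood placed on a Whatmann filter paper", with qRT-PCR planned on them.

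**The concern.** By design, an asymptomatic infection in a control woman is left alone, and Protocol 1.2 itself expects undetected low-level infection to become chronic. The same infection in an intervention woman is found and treated, after which she can be infected again. Screening therefore mainly shortens infections, and a count of infections does not measure duration.

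Take two women with four tests each, both infected before test 1 and both exposed again between tests 2 and 3.

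- Control: positive, positive, positive, positive. One episode, four positive visits.
- Intervention: positive (treated), negative, positive (treated), negative. Two episodes, two positive visits.

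The intervention/control ratio is 2/1 = 2 for episodes and 2/4 = 0.5 for positive visits. If the second infection had already shown at test 2, a positive-after-negative rule would give the intervention woman one episode, and a rule treating every post-treatment positive as new would give her two.

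This is the only SAP model described as assessing screening. The regressions that follow in Section 6.2 relate birth outcomes to malaria status, not to arm. If the rule is chosen once data are in hand, so is the direction of the result.

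**Working it through.** **The plan's own figure.** The documents give no figure for the infection model. The only related one is the sample size for low birth weight (LBW). With 17.3% against 12.3%, 3:1 allocation, two-sided 5%, 80% power and continuity correction, it is 538 + 1614 = 2152, and 2152 × 1.20 = 2582.4, rounded up to 2583. It reproduces and contains no infection count, so it is not affected.

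**Main check.** A weekly simulation used 200,000 women per arm over gestational weeks 16 to 40, with tests at weeks 16, 26, 32, 37 and 40. Weeks 26, 32, 37 and 40 approximate the visits in Protocol Table 5. The other inputs are assumptions:

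- weekly risk of a new infection h = 0.5% to 4%, equal in both arms;
- mean untreated duration d = 4 to 40 weeks;
- proportion infected at the first test hd/(1 + hd);
- test sensitivity 95%, the same test in both arms;
- all infections asymptomatic; intervention positives cleared at the visit, control infections untreated.

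Episodes: consecutive control positives count once, and each intervention positive counts as new because the previous one was cleared. Positive visits: every positive counts. In the intervention arm the two counts coincide. Ratio = intervention mean / control mean.

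| h, d | Control episodes | Control positive visits | Intervention count | Episode ratio | Visit ratio | Weeks-infected ratio |
|---|---|---|---|---|---|---|
| 0.5%, 40 | 0.273 | 0.797 | 0.272 | 1.00 | 0.34 | 0.17 |
| 1%, 40 | 0.464 | 1.352 | 0.495 | 1.07 | 0.37 | 0.19 |
| 2%, 20 | 0.577 | 1.358 | 0.659 | 1.14 | 0.49 | 0.30 |
| 4%, 4 | 0.513 | 0.657 | 0.567 | 1.11 | 0.86 | 0.69 |
| 4%, 40 | 0.977 | 2.925 | 1.380 | 1.41 | 0.47 | 0.28 |

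Over all 16 combinations the episode ratio was 1.00 to 1.41 and the visit ratio 0.34 to 0.86. Weeks infected fell by 31% to 83%. Ever-positive (yes/no) gave 0.99 to 1.01, so that outcome does not show the benefit either.

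**Other simulations.** These used acquisition per visit interval (5% to 20%), persistence to the next visit of 0.3 to 0.8, and 2 to 5 tests per woman where the number was recorded.

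- Positive-after-negative in both arms: 1.03–1.15, 1.02–1.12 and 1.01–1.10 in three separate runs.
- Every post-treatment positive new: 1.06–1.43, 1.15–1.42 and 1.07–1.33.
- Positive visits: 0.56–0.86, 0.53–0.85 and 0.53–0.85.

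**Unequal detection.** Next, control infections were detected with 25% sensitivity at every visit, which is the phase 2 microscopy figure in Protocol Table 3, and intervention infections with 95%. With weekly risk 1% to 2% and duration 10 to 20 weeks, the episode ratio was 2.05 to 2.65 and the visit ratio 1.74 to 2.34, although weeks infected fell to 0.27–0.42 of control. Both counts then point against screening.

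**The case against.** A reader might infer that the SAP counts an untreated control infection once and so penalises successful treatment. The documents do not support that. They state no rule. Counting episodes is a natural reading of the wording, but counting each positive visit is also open and reverses the sign.

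The reversal is also modest. Under positive-after-negative the largest ratio is 1.15. With a simulated standard error of 0.0752 at 538/1614 women, ln(1.15)/0.0752 = 0.140/0.0752 = 1.9 standard errors. At weekly risks of 0.5% to 1% the main check gives a rise of 0% to 7%. Larger values need the post-treatment-new rule or high transmission. All of this stands. It limits the claim to no visible reduction or a modest rise under an episode count.

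The counting rule need not be the larger fault: if control counts come from routine tests, unequal detection may matter more. That stands too, and the fix must deal with both. The missing denominator matters little for precision: a log(tests) offset moved the standard error only from 0.0752 to 0.0741.

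Finally, the main arm comparison does not rest on this model. Protocol 5.8 plans risk ratios by arm for the primary outcome, and SAP Section 6.1 has a composite of infection at delivery that needs no episode count. This makes the gap secondary but does not fill it, because delivery is a single time point and the model in question is meant to cover the pregnancy.

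One limit: the SAP cites protocol version 1.5, and the protocol reviewed is version 1.1, so a later sampling schedule cannot be checked.

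**Conclusion.** The point holds as a definition gap in a secondary analysis, and it should be closed before outcomes are compared by arm. With the same test in both arms, an episode count shows no reduction or a modest rise: about 1.0 to 1.15 for positive-after-negative, and up to about 1.4 if every post-treatment positive is new or transmission is high. A count of positive visits shows a reduction, 0.34 to 0.86, from the same process. If routine tests supply the control count, either version is biased against screening.

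The sizes rest on assumed acquisition and persistence, equal risk in the two arms, and clearance at treatment; the documents give none of these as figures. That the sign turns on the counting rule held in every simulation that compared the two counts, apart from scenarios where the episode ratio was simply 1.00. A reader might go on to doubt the trial's primary conclusion. Nothing here supports that: LBW and the 2583 are unaffected.

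**What to change.** In SAP Section 6.2, replace the count as the measure of screening effect with a visit-level outcome:

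- **Outcome:** P. falciparum qRT-PCR positive (yes/no) on the DBS from each scheduled visit after enrolment through delivery, in both arms.
- **Model:** log-link GEE clustered on the woman, with arm, visit, parity stratum and site. Report the prevalence ratio with its 95% confidence interval.
- **Enrolment test:** use it as a baseline covariate or report it separately. It precedes any treatment, and pooling it dilutes the effect; in two simulated scenarios the ratio moved from 0.48 to 0.57 and from 0.55 to 0.63.
- **Two versions:** keep all P. falciparum and submicroscopic only, with submicroscopic defined by the same tests in both arms. Protocol 5.2 limits control-arm diagnosis by microscopy to symptomatic women, while 5.7.2 describes films and an RDT drop from each participant, so the sponsor should state which results will exist.
- **Description:** report positive visits / visits tested by arm, and new episodes under a stated rule.

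The cost is SAP wording and standard Stata or R code, using samples and qRT-PCR already planned. There are two conditions. The estimate is infection prevalence over pregnancy, not incidence, and must be labelled so. The sponsor must also confirm that DBS are taken at every scheduled visit in both arms, because Protocol 5.7.2 says only that all individuals are sampled; if they are not, extra sampling or fewer visits in the analysis would follow.
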